Methodology	This is a single arm Phase 2 study. Stage 1 and 2 of the study are monotherapy evaluations of ADXS11-001 in 31 and 24 subjects, respectively with persistent/recurrent, loco-regional or metastatic SCCA of the anorectal canal that have received at least 1 regimen for the treatment of advanced disease. Additionally, those deemed by their investigator as not optimal candidates for chemotherapy would be considered eligible.

Study Title:	Phase 2 Study of ADXS11-001 In Subjects with Persistent/Recurrent, Loco-Regional or Metastatic Squamous Cell Carcinoma of the Anorectal Canal
	In addition, all subjects will participate in a 3 year Lm surveillance period. The surveillance period will begin following the last dose of study treatment or at the time of study discontinuation. This period is intended to help ensure the eradication of Lm bacteria. This period will also include a 6 month course of trimethoprim/sulfamethoxazole which will be initiated approximately 72 hours after the completion of the last dose of ADXS11-001 or immediately following study discontinuation.
Objectives	
Primary:
 
 • To evaluate efficacy as measured by the overall response rate and rate of 6 month progression-free survival (PFS) in subjects with persistent/recurrent, loco-regional or metastatic SCCA of the anorectal canal as determined by RECIST 1.1. 
Secondary:
 
 • To evaluate efficacy as measured by the overall response rate and rate of 6 month PFS in subjects with persistent/recurrent, loco-regional or metastatic SCCA of the anorectal canal as determined by irRECIST. • To evaluate the safety and tolerability of ADXS11-001 in subjects with persistent/recurrent, loco-regional or metastatic SCCA anorectal canal SCCA of the anorectal canal by NCI CTCAE 4.0 • To evaluate the additional parameters of efficacy (duration of response, PFS and overall survival) of ADXS11-001 in subjects with persistent/recurrent, loco-regional or metastatic SCCA of the anorectal canal as determined by RECIST 1.1 and irRECIST.
Criteria for Evaluation	
Safety: recorded AEs, changes in physical examinations, vital signs measurements, clinical laboratory evaluations and Lm surveillance monitoring.
 
Efficacy: Response rates as measured by RECIST 1.1 and irRECIST, duration of response, PFS

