4.2.2 Delayed/Late *Listeria* Infection

In a Phase 1 clinical study, in the absence of antibiotics, *Lm* was rapidly cleared from the blood. No *Lm* was detected in the blood, urine or feces of any subject beyond 48 hours post-dosing and at the highest dose of ADXS11-001 tested (1×10^{10} CFU).[13]

wt-Lm is known to form and persist within biofilms especially on medical devices despite antibiotic treatment.[14] Although rare, medical device-related infections such as ventriculo-peritoneal shunt infection, peritoneovenous shunt infection, and prosthetic joint infection have been reported.[15-18] ADXS11-001 is highly sensitive to antibiotics such as ampicillin and trimethoprim/sulfamethoxazole which can be an effective treatment regimen for listeria infection. Therefore, subjects with implanted medical device(s) that pose a high risk for colonization and/or cannot be easily removed are excluded from this study. In addition, all subjects will receive a course of oral antibiotics beginning on Day 4 (approximately 72 hours) after each dose of ADXS11-001 and for 6 months following the last dose of ADXS11-001 to aid in the eradication of the bacteria.

[figure not shown]
[figure not shown]

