5.6.4 Management and Surveillance of Listeria During Study Participation

A subject who experiences a fever (CTCAE Grade 1 or greater) 24 hours following the completion of ADXS11-001 infusion should be started on NSAIDs, hydration and other appropriate measures to treat the fever. In the event that the fever persists or worsens 48 hours following the completion of ADXS11-001 infusion then oral or broad spectrum IV antibiotics should be considered based on the subject's medical condition. If the fever remains unresponsive to oral/IV antibiotics 72 hours following the completion of the infusion then a blood culture should be obtained to evaluate for listeremia and determine the appropriate treatment course for the subject.

All subjects will receive a 6 month course of an oral antibiotic regimen as a prophylactic measure approximately 72 hours following the completion of the last dose of ADXS11-001 treatment or at the time of study discontinuation. This additional safety measure is intended to eradicate *Lm* from the body.

Lm surveillance monitoring will also be initiated following the completion of the last dose of ADXS11-001 treatment or at the time of study discontinuation. This monitoring will include obtaining a blood sample for CBC, CMP, including CRP and ESR, and blood cultures for the detection of listeria. Testing will be performed on all subjects who have received at least one dose of ADXS11-001 and occur every 4 months (± 2 weeks) for 3 years.

Should a diagnosis of listeriosis occur at any point after treatment with ADXS11-001 is completed immediate, intensive IV antibiotic treatment (e.g. Ampicillin +/- Gentamicin or other IV antibiotic regimen as indicated) is required. An infectious disease consult should be obtained. Based on each individual subject's case and at the discretion of the treating physician, the removal of any foreign medical object that has been present since treatment with ADXS11-001 was initiated may be warranted. It is extremely important that the investigator, his/her research staff, other healthcare providers involved in the care of the subject as well as each subject participating in this study are educated and made aware of the signs and symptoms of listeriosis and the potential for delayed listeremia/listeriosis. Educational materials for the investigator, research staff, health care providers and patients will be prepared and educational training performed.

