⁸ All Subjects will receive a 7-day course of oral antibiotic therapy starting approximately 72 hours after administration of ADXS11-001. All subjects will also receive an additional 6 month oral antibiotic course to be initiated approximately 72 hours following the last dose of study treatment or anytime upon discontinuation of study treatment.

⁹ Adverse events and serious adverse events will be assessed from the time Informed Consent is obtained through 30 days after the last ADXS11-001 infusion is administered.

¹⁰ Height will be measured at screening only. Monitor vital signs immediately [REDACTED] for the first 4 hours following the completion of every ADXS11-001 infusion.

¹¹ CID1 Safety labs do not need to be repeated if screening labs are collected within 3 days of dosing. All laboratory procedures are to be completed and assessed by the investigator within 3 days prior to the administration of ADXS11-001 to confirm lab criteria for study treatment are met.

¹² Urine pregnancy tests must be performed within 72 hours prior to each ADXS11-001 infusion for female subjects of childbearing potential. If the urine test is positive or cannot be confirmed as negative, a serum pregnancy test will be required.

¹³ *Lm* Surveillance Monitoring will include a 6-month course of oral antibiotics and routine monitoring of CBC, CMP (including CRP, ESR) and blood cultures. Following completion of the last dose of study treatment or following study discontinuation, all assessments will be performed every 4 months (±2 weeks) for 3 years.

¹⁴ Baseline tumor imaging and assessments must be performed within 28 days prior to the first ADXS11-001 infusion in the first study cycle. Subsequent tumor imaging and assessments will be conducted at Week 8 (±1 week) for the duration of study participation. Radiologic progression, not accompanied by clinical deterioration, should be confirmed ≥4 weeks later.

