(1) During Study Treatment Phase - All subjects will receive a 7 day course of oral antibiotic therapy starting approximately 72 hours (Day 4) after administration of ADXS11-001. Antibiotic therapy should consist of either 160 mg trimethoprim/800 mg sulfamethoxazole (DS) tablet administered three times during the 7 consecutive days or 80 mg trimethoprim/400 mg sulfamethoxazole administered daily for 7 consecutive days or for subjects with sulfa allergies, ampicillin 500 mg four times daily for 7 consecutive days. ADXS11-001 is resistant to both streptomycin and chloramphenicol. In the event a subject experiences a persistent fever present at 72 hours after receiving ADXS11-001, the oral regimen will be replaced by broad spectrum IV antibiotics administration- until a blood culture is obtained and results are available. At this time, a specific IV antibiotic regimen may be prescribed based on the results of the blood culture. Should a diagnosis of listeriosis be made intensive IV antibiotic treatment must be initiated. Ampicillin +/- Gentamicin is the preferred treatment regimen but other IV antibiotics may be used based on the subject's tolerance, culture and sensitivity results. An ID consult should be obtained.

(2) Post Study Treatment - All subjects will receive a 6 month course of oral trimethoprim/sulfamethoxazole or ampicillin for subjects with sulfa allergies to be initiated approximately 72 hours following the last dose of study treatment or at the time of study discontinuation. Trimethoprim/sulfamethoxazole therapy should consist of either 160 mg trimethoprim/800 mg sulfamethoxazole (DS) tablet administered three times a week or 80 mg trimethoprim/400 mg sulfamethoxazole administered daily for 7 consecutive days. The dose of ampicillin consists of 500 mg four times daily for 6 months.

Tumor Imaging/Disease Assessment - CT scan or MRI for determination of unidimensional measurements and disease response. Imaging studies and tumor assessments will be performed every 9 weeks starting at Week 8 of Cycle 1.

Pregnancy test - A rapid pregnancy test will be performed within 72 hours of each treatment administration (combination or monotherapy) for all women of child bearing potential prior to treatment. A positive rapid pregnancy test must be confirmed, prior to dosing, by a serum pregnancy test (minimum sensitivity 25 IU/L or equivalent units of β HCG).

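### The post-treatment antibiotic instruction limits the 80/400 mg trimethoprim/sulfamethoxazole option to 7 days, contradicting the 6-month course required in the same paragraph and elsewhere

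*Combined protocol and SAP*

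**What the plan says.** Section 7.1.6.2 has two numbered antibiotic instructions.

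- **Item (1), during treatment.** A 7-day course follows each infusion. The lower-strength option is "80 mg trimethoprim/400 mg sulfamethoxazole administered daily for 7 consecutive days or for subjects with sulfa allergies", and those subjects take ampicillin for the same 7 days.
- **Item (2), after treatment.** The lead sentence sets the duration: "All subjects will receive a 6 month course of oral trimethoprim/sulfamethoxazole or ampicillin for subjects with sulfa allergies". The next sentence gives the two trimethoprim/sulfamethoxazole schedules: "DS) tablet administered three times a week or 80 mg trimethoprim/400 mg sulfamethoxazole administered daily for 7 consecutive days". The last sentence covers the sulfa-allergy alternative: "The dose of ampicillin consists of 500 mg four times daily for 6 months".

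The duration is repeated elsewhere in the protocol:

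- Section 1 (Summary), Methodology: "This period will also include a 6 month course of trimethoprim/sulfamethoxazole". The Duration of Participation entry also gives 6 months.
- Section 4.2.2: "for 6 months following the last dose of ADXS11-001 to aid in the eradication of the bacteria".
- Section 5.6.4: "All subjects will receive a 6 month course of an oral antibiotic regimen as a prophylactic measure".
- Section 6.1, footnote 8: "All subjects will also receive an additional 6 month oral antibiotic course". This is listed in addition to the 7-day course after each dose. Footnote 13 also gives 6 months.
- Section 7.1.6.3 describes the surveillance phase as including a 6-month oral course.

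**The concern.** One of the three post-treatment regimens carries a duration of 7 days inside a paragraph whose purpose is to prescribe 6 months. The other places state how long the course lasts but not the dose or frequency, so a site writing the prescription has only this paragraph to work from.

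The course is a safety measure. Section 5.6.4 describes it as intended to eradicate the vector, and Section 4.2.2 places it under delayed or late *Listeria* infection. Both the routine 7-day course and the post-treatment course start about 72 hours after the last infusion. Taken literally, the lower-strength post-treatment option is therefore identical to the routine course already given after each dose, and the additional course in footnote 8 of Section 6.1 disappears for any subject prescribed it that way.

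**Working it through.** The plan has no computed figure to reproduce here. The check compares the wording of the options and then counts doses.

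**1. Wording of the options in the two items of Section 7.1.6.2**

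| Option | Item (1), after each infusion | Item (2), after treatment ends |
|---|---|---|
| Double-strength, 160/800 mg | three doses within 7 days | three doses per week, no end point stated |
| 80/400 mg | daily, 7 consecutive days | daily, 7 consecutive days (unchanged) |
| Ampicillin 500 mg, four times daily | 7 consecutive days | 6 months |

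The double-strength and ampicillin options were both reworded for item (2). Only the 80/400 mg option was not, which points to a carry-over error.

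**2. Doses under the literal and the intended reading**

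Assumption: six calendar months is 181 to 184 days, depending on the start date.

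- Intended: one dose daily, 181 to 184 doses.
- Literal: 7 doses.
- Doses missed: 181 − 7 = 174, up to 184 − 7 = 177.
- Share of the course given: 7/184 = 3.8% to 7/181 = 3.9%.

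**3. Do the two trimethoprim/sulfamethoxazole options match in total dose?**

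Trimethoprim, item (1), per course:

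- 80 mg × 7 = 560 mg
- 160 mg × 3 = 480 mg
- Ratio 560/480 = 1.17

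Trimethoprim, item (2), over 6 months:

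- Double-strength: 3 × 181/7 to 3 × 184/7, about 78 to 79 doses; at 160 mg each, 12.4 to 12.6 g
- 80 mg daily for 6 months: 80 × 181 to 80 × 184 = 14.5 to 14.7 g
- Ratio 14.5/12.4 = 14.7/12.6 = 1.17, the same as in item (1)
- 80 mg daily for 7 days: 560 mg, or 4.4% to 4.5% of the double-strength total (560/12,617 to 560/12,411)

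The two options stand in the same relation as in item (1) only if the 80/400 mg option runs daily for the full 6 months. This agrees with the duration stated everywhere else and shows that the 7-day limit cannot be intended.

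**The case against.** The strongest reply is that the paragraph can be read coherently. Its first sentence fixes the duration at 6 months, and the next only says how that course is delivered. The double-strength option was changed to a weekly schedule, so the 80/400 mg clause beside it could mean every day of the week, repeated until the 6 months are up. The dose ratio of 1.17 fits that reading. No other text supports a one-week post-treatment course, and a careful prescriber would probably give 6 months.

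There are also chances to notice an early stop. Protocol-mandated antibiotics go into the eCRF, concomitant medication is recorded to 30 days after the last dose, and a course begun at about 72 hours and stopped after a week would end near day 10, inside that window. Section 5.6.4 also requires education on delayed listeriosis.

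Much of this stands. The intent is clear and the risk is limited to literal readers. The weekly reading itself is weak, though. Daily already means every day, so the 7 days add nothing unless they are a duration. The clause does not say that the pattern repeats each week. The identical words in item (1) mean a total of 7 days. The recording and follow-up steps might catch a mistake, but they do not correct the instruction that causes it.

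**Conclusion.** The concern holds. The 80/400 mg clause in item (2) states a duration that conflicts with its own lead sentence and with Sections 1, 4.2.2, 5.6.4, 6.1 and 7.1.6.3. It is a drafting error, but it sits in operative dosing text for a safety measure that applies to all subjects, so it should be fixed.

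The size is conditional. A subject treated by the literal wording would miss 174 to 177 doses and receive under 4% of the planned course, taking 6 months as 181 to 184 days. The documents do not allow an estimate of how many subjects would be affected. Sample size, power, type I error, the efficacy endpoints and the surveillance culture schedule are untouched.

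**What to change.** In Section 7.1.6.2, item (2), change the 80/400 mg option so that it reads as daily dosing for 6 months. In the same sentence, add a 6-month duration to the three-times-weekly double-strength option. The lead sentence already governs that option, so this second change is for clarity: all three regimens then state both frequency and duration. Leave item (1) as it is.

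Send sites a short letter pointing out the correction. The cost is one sentence in a protocol amendment and the letter; no analysis or visit schedule changes.

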7.1.6.3 Safety Follow-up/Post-Treatment Visits

Safety follow-up will be conducted via telephone call 30 days (± 5 days) after the last ADXS11-001 infusion to confirm the resolution of any ongoing AEs and SAEs. Additional unscheduled visits may be considered as needed and at the discretion of the investigator.

Surveillance monitoring for the detection of *Lm* will be initiated at the completion of study treatment according to the protocol or at the time of study discontinuation if earlier. This surveillance monitoring phase will consist of a 6 month course of oral antibiotics, obtaining a blood sample to monitor CBC, CMP, including CRP and ESR, and blood cultures at regular intervals. This testing will be performed on all subjects who have received at least one dose of ADXS11-001. It will occur every 4 months (± 2 weeks) for 3 years beginning after the last dose of study treatment. If a persistent increase in CRP and/or ESR is observed with negative blood cultures for listeria during this time the subject should be evaluated and treated, as appropriate, for another possible cause. In the event that a definite cause has not been identified then subjects must continue to be monitored closely, including another additional testing and a blood culture, for possible signs/symptoms of listeriosis. This testing may be performed at the investigative site or at another acceptable location following consultation with the Sponsor.

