1 SUMMARY

Study Title:	Phase 2 Study of ADXS11-001 In Subjects with Persistent/Recurrent, Loco-Regional or Metastatic Squamous Cell Carcinoma of the Anorectal Canal
Trial Phase	Phase II
Clinical Indication	Persistent/recurrent, loco-regional or metastatic squamous cell carcinoma (SCCA) of the anorectal canal
Trial Type	Interventional
Study Centers	Multicenter, USA
Route of Administration	Intravenous (IV)
Trial Blinding	Open label, unblinded
Number of Trial Subjects	Approximately 55 
 • 31 subjects in Stage 1 • 24 subjects in Stage 2
Estimated Duration of Trial	Approximately 6 years
Duration of Participation	Each subject will participate in the study for an average of approximately 6 years from the time the subject signs the informed consent form (ICF) through the final contact. Treatment will continue for up to 2 years or until the subject meets a discontinuation criterion (e.g., has either documented progression, unacceptable adverse events (AEs), withdrawn due to investigator's discretion, subject withdraws consent, pregnancy, or noncompliance with study procedures or treatments). Subjects who have been on therapy for >6 months and who attain a complete response (CR) may consider stopping the trial. Subjects who achieve a CR should receive at least 1 additional cycle of treatment. The study duration includes an active study treatment phase which may last up to a maximum of 36 months and a 3 year Lm Surveillance Monitoring Phase, which includes 6 months of oral antibiotic administration to commence upon completion of the active study treatment phase or upon study discontinuation. All subjects will be followed for adverse and serious adverse events (SAEs) for a minimum of 30 days. End of Study will be defined as 1 year after the last subject is enrolled on study. However, any ongoing subject, subjects who are still deriving clinical benefit from ADXS11-001 therapy at the end of their 2 year treatment period or at the end of the study may be enrolled into a separate extension study, as available.
Randomization Ratio	None

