4.2.4 Study Stopping Rules

Rules for temporary suspension of study for death due to non-progressive disease, hematologic and non-hematologic events related to ADXS11-001 treatment

The Advaxis medical monitor and Project Manager as well as other key personnel associated with the trial (e.g. CRO Medical Monitor, Primary Investigator), as appropriate, will monitor death due to non-progressive disease and hematologic and non-hematologic toxicities for individual subjects in real-time and trial-level cumulative toxicities on a monthly basis. These events must be deemed by the Investigator at the site to have some degree of “relatedness” to ADVXS11-011 treatment (e.g. definitely, probably or possibly related) in order to be considered for evaluation. The assessment of cumulative trial-level toxicities will not begin until at least 5 subjects have received a dose of ADXS11-001 and evaluated for death and individual toxicity events following the completion of the initial 3-week treatment period. The guidelines below will be used to determine the threshold of cumulative events that will result in temporary suspension of enrollment for new subjects and dosing for any active subject until a thorough of the cumulative information is evaluated and a risk/benefit assessment conducted.

- Death (other than death related to disease progression) that occurs within 30 days of the ADXS11-001 infusion
-

- >30% Grade 3 or greater non-hematologic adverse events that are at least possibly related to ADXS11-001
- >30% Grade 4 or greater hematologic adverse events that are at least possibly related to ADXS11-001

The assessment of an individual subject event which meets the criteria as defined above and has been determined by the investigator to be related to ADXS11-001 treatment will begin as soon as all required and relevant information is received. The same project team personnel will review all of the information and determine an appropriate course of action (e.g., temporarily suspending enrollment and ongoing treatment in active subjects; temporarily suspending enrollment and allowing treatment in active subjects to continue) based on a thorough review pertaining to the event.

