6 STUDY EVALUATIONS

6.1 Schedule of Events

Study Procedure	Screening ²	9 Week Treatment Cycle ¹									End of Therapy ³	Follow-Up
		Weeks										
		1	2	3	4	5	6	7	8	9		
Administrative Procedures												
Informed consent	X											
Eligibility Criteria / Subject ID Card	X											
Demographics/Medical History	X											
Prior Cancer History	X											
Prior/Concomitant Therapies & Procedures	X	X			X			X			X	X ⁴
Prophylactic Medication ⁶		X			X			X				
ADXS11-001 Administration ⁷		X			X			X				
Dispense/Prescribe Oral Prophylactic Antibiotics ⁸		X			X			X				X
Phone Call												X ^{4,5}
Clinical Procedures/Assessments												
Review Adverse Events ⁹	X	X			X			X			X	X ⁴
Vital signs/Weight ¹⁰	X	X			X			X			X	
Physical Examination	X	X			X			X			X	
ECOG Performance Status	X	X			X			X			X	
Laboratory Procedures/Assessments¹¹												
CBC with Differential	X	X			X			X			X	
Serum Chemistry Panel	X	X			X			X			X	
Coagulation Profile	X	X			X			X			X	

Study Procedure	Screening ²	9 Week Treatment Cycle ¹									End of Therapy ³	Follow-Up
		Weeks										
		1	2	3	4	5	6	7	8	9		
Urine Dipstick	X	X			X			X			X	
Urine Pregnancy Test ¹²	X	X			X			X			X	
Lm Surveillance Monitoring ¹³												X
Efficacy Measurements												
Tumor Imaging ¹⁷	X							X				

¹ Repeating 9-week treatment cycles. Study cycles will be numbered sequentially.

² Screening/Baseline tumor evaluations will be performed within 28 days prior to first dose of study treatment.

³ End of Therapy is not a visit. Assessments noted here must be completed upon the decision to discontinue a subject from study treatment.

⁴ Safety Follow-Up will be conducted via a telephone call *30 days (± 5 days) after the last ADXS11-001 infusion* to confirm the resolution of any new or ongoing adverse events and serious adverse events. All ongoing events must be followed through resolution.

⁵ Survival Follow-Up will be conducted at each visit during the *Lm Surveillance period* and via a telephone call *every 3 months (± 2 weeks) after the Lm Surveillance period* to determine survival status for all study subjects.

⁶ Subjects will be pretreated with prophylactic regimen at least [REDACTED] before each ADXS11-001 infusion.

⁷ The initial ADXS11-001 administration will identify Day 1 of Cycle 1. ADXS11-001 may be administered ± 7 days within each scheduled infusion.

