7.2 Assessing and Recording Adverse Events

An AE is defined as any untoward medical occurrence in a patient or clinical investigation subject administered a pharmaceutical product and which does not necessarily have to have a causal relationship with this treatment. An AE can therefore be any unfavorable and unintended sign (including an abnormal laboratory finding, for example), symptom, or disease temporally associated with the use of a medicinal product or protocol-specified procedure, whether or not considered related to the medicinal product or protocol-specified procedure. Any worsening (i.e., any clinically significant

adverse change in frequency and/or intensity) of a preexisting condition that is temporally associated with the use of the Sponsor's product, is also an AE.

Changes resulting from normal growth and development that do not vary significantly in frequency or severity from expected levels are not to be considered AEs. Examples of this may include, but are not limited to, onset of menses or menopause occurring at a physiologically appropriate time.

The Sponsor's product includes any pharmaceutical product, biological product, device, diagnostic agent or protocol-specified procedure, whether investigational (including placebo or active comparator medication) or marketed, manufactured by, licensed by, provided by or distributed by Advaxis for human use.

AEs may occur during the course of the use of Advaxis' product in clinical trials or within the follow-up period specified by the protocol, or prescribed in clinical practice, from overdose (whether accidental or intentional), from abuse and from withdrawal.

AEs may also occur in screened subjects during any pre-allocation baseline period as a result of a protocol-specified intervention, including washout or discontinuation of usual therapy, diet, placebo treatment or a procedure.

All AEs will be recorded from the time the consent form is signed through 30 days following cessation of treatment on the Adverse Event CRF forms/worksheets. The reporting timeframe for AEs meeting any serious criteria is described in [Section 7.2.3.1](#).

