8.5 Analysis of Safety Data

All AEs will be summarized by patient, treatment, and prior recurrence history (aggressive [recurrence within 2 years]/non-aggressive).

The NCI CTCAE v 4.0 will be used for AE grading (Grades 1 to 4). AEs will be classified using the Medical Dictionary for Regulatory Activities (MedDRA®) coding system.

The overall incidence of AEs will be summarized and classified by body system and by treatment group. An AE will be summarized if the onset date occurs anytime during study treatment or up to 30 days after the last dose of study treatment; or, if it occurs prior to Day 1 and worsens while on therapy. The type, incidence, severity, and causality of each AE, the duration of the event, and any required treatment interventions will be tabulated.

Physical examination results will be presented in the patient data listings. Vital sign measurements will be summarized at each infusion using descriptive statistics. The incidence of clinically significant laboratory abnormalities will be presented, and laboratory data will be summarized at each infusion by the NCI CTCAE v 4.0 toxicity grades. Laboratory data will be presented for patients having Grade 3 or 4 changes from baseline.

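### The safety call, the only scheduled AE review at a fixed time after the last infusion, may be made on Days 25–29, before the 30-day AE window closes

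*Combined protocol and SAP*

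**What the plan says.** The post-treatment safety call appears in three places with the same timing: Section 2, footnote 4 of the Schedule of Events (Section 6.1) and Section 7.1.6.3. Each sets it at 30 days (± "5 days) after the last ADXS11-001 infusion to confirm the resolution of any ongoing AEs and SAEs", as Section 7.1.6.3 puts it. The stated purpose differs. Sections 2 and 7.1.6.3 mention only ongoing events, while footnote 4 says the call is "to confirm the resolution of any new or ongoing adverse events and serious adverse events".

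The collection and analysis windows run to 30 days:

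- Schedule footnote 9: "Adverse events and serious adverse events will be assessed from the time Informed Consent is obtained through 30 days after the last ADXS11-001 infusion".
- Section 7.2: "All AEs will be recorded from the time the consent form is signed through 30 days following cessation of treatment". Sections 7.1.2.1 and 7.2.3.1 use the same 30-day limit for assessment and for SAE reporting.
- Section 8.5: "An AE will be summarized if the onset date occurs anytime during study treatment or up to 30 days after the last dose".
- Section 1: "All subjects will be followed for adverse and serious adverse events (SAEs) for a minimum of 30 days".
- Section 4.2.4 lists, among its suspension criteria, a death not due to progression "that occurs within 30 days of the ADXS11-001 infusion".

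After the call, the next contact with a set time is the first *Lm* surveillance visit. These visits run every 4 months (±2 weeks) for 3 years and collect laboratory tests, blood cultures and survival status.

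**The concern.** A contact that closes a data-collection period should not be allowed before the period ends. Here it is. A site can call on Day 25, stay within the visit window, and have no further scheduled occasion to ask about AEs in the last days of the window that Section 8.5 tabulates.

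The main stake is completeness of the safety tables. They would be read as covering 30 days after the last dose for everyone, while some subjects had a scheduled enquiry over fewer days, short of the minimum in the Summary. Non-serious AEs are the most exposed, because nothing later in the schedule asks about them. The period is not empty of exposure: the 6-month oral antibiotic course starts about 72 hours after the last dose.

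The second stake is timing. A death or SAE between an early call and Day 30 falls inside the 24-hour reporting period of Section 7.2.3.1 and, if judged related, inside the scope of Section 4.2.4. Yet the schedule may not bring it to the site's notice for months.

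**Working it through.** **Inputs.** Call: Day 30 ± 5 (Section 2, Schedule footnote 4, Section 7.1.6.3). AE window: through Day 30 after the last dose (Schedule footnote 9, Sections 7.1.2.1, 7.2, 7.2.3.1 and 8.5). First *Lm* visit: 4 months ± 14 days (Sections 5.6.4 and 7.1.6.3). The Summary does not name the start of its 30-day minimum. I read it as the last dose, in line with the other sections.

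**Step 1: the permitted call days.** Earliest = 30 − 5 = Day 25. Latest = 30 + 5 = Day 35.

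**Step 2: the gap.** Days left in the AE window after a call on day d = max(0, 30 − d).

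| Call day | 25 | 26 | 27 | 28 | 29 | 30–35 |
|---|---|---|---|---|---|---|
| Days left | 5 | 4 | 3 | 2 | 1 | 0 |

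The worst case is 5/30 = 16.7% of the window. This needs no assumption.

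**Step 3: does another scheduled contact close the gap?**

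- *Follow-Up column, Schedule of Events.* The AE review entry carries footnote 4 only, which is this call.
- *End of Therapy.* It includes AE review, but footnote 3 says it is not a visit and ties it to the decision to stop treatment. It has no fixed day after the last infusion, so it may fall before Day 25.
- *Unscheduled visits.* Section 7.1.6.3 leaves these to the investigator's discretion.
- *Lm surveillance.* 4 × (365.25/12) = 121.75 days; 121.75 − 14 = 107.75 and 121.75 + 14 = 135.75. The first visit is at about Day 122 (range 108–136). The Schedule lists no AE review there.

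None is guaranteed to cover Days 26–30 for AEs.

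**Step 4: deaths.** Survival status is collected at each *Lm* visit (Section 7.1.6.4). If the schedule were the only source of information, a death on Days 26–30 would be learned of between 108 − 30 = 78 and 136 − 26 = 110 days later.

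**Step 5: an illustration of the average.** The documents do not say how call days will be distributed. If they were spread evenly over the 11 permitted days (assumed), 5/11 = 45% of calls would precede Day 30. The mean uncovered time over all subjects would be (5 + 4 + 3 + 2 + 1)/11 = 15/11 = 1.4 days, or 1.36/30 = 4.5% of the window. If every call were on Day 30 or later it would be 0; if every call were on Day 25 it would be 5 days.

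**Step 6: after a one-sided window.** Earliest call = Day 30, so the gap is 0.

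**The case against.** The strongest reply is that a contact window is not the collection obligation. Schedule footnote 9 and Sections 7.1.2.1, 7.2 and 7.2.3.1 require assessment, recording and SAE reporting through 30 days whatever day the call is made, so a site that calls on Day 25 and then stops has not met them. That is correct. The weakness is narrower: the schedule contains no contact sure to discharge the duty, and a site can follow the schedule exactly while falling short of it.

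The likely loss is also small. The plan describes typical reactions as starting 2–4 hours after infusion and usually resolving within 12–24 hours, and delayed listeriosis has its own 3-year surveillance. The share of AEs lost is therefore probably well below 17%, which measures calendar time and not events. The gap also concerns only the last dose, since each earlier dosing visit includes AE review.

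Four stronger readings might be inferred, and the documents do not support them:

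- *That deaths on Days 26–30 are missed.* Survival status is collected for all subjects at the *Lm* visits. The risk is delay, not loss.
- *That the call is the only post-treatment safety contact.* End of Therapy includes AE review, and *Lm* surveillance is itself a listed safety evaluation. The call is the only scheduled AE review at a fixed time after the last infusion.
- *That such a death would trigger a mandatory suspension which an early call defeats.* Section 4.2.4 counts only events the investigator judges at least possibly related, and an individual event leads to a team decision on the course of action. Section 7.2.3.1 also makes related SAEs reportable at any time, although only once they come to the investigator's attention.
- *That nearly half of subjects will be called early.* The 45% rests wholly on the assumed even spread.

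**Conclusion.** The point stands as a minor internal conflict. The permitted call window opens 5 days before the AE window closes, and no later scheduled AE review makes up the difference. The size is up to 5 of 30 days for a subject called on Day 25, with possible under-collection of late-onset AEs and possible delay in learning of a death. The number of events affected cannot be derived from the documents.

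The conclusion rests on the Schedule as printed, with AE review in the Follow-Up column tied to footnote 4, and on sites following the schedule without extra contacts. The differing purpose of the call is a separate wording conflict that matters whatever day the call is made: on the text of Sections 2 and 7.1.6.3 alone, even a Day 35 caller is not told to ask about new events, although footnote 4 includes them. No efficacy endpoint or stage decision is affected.

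**What to change.** In Section 2, Schedule footnote 4 and Section 7.1.6.3:

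1. Change the call window to 30 days (+5 days) after the last infusion.
2. State the same purpose in all three: to ask about new as well as ongoing AEs and SAEs through Day 30.

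The uncovered period falls from up to 5 days to 0, and the call then meets the 30-day minimum in the Summary. The cost is that some calls are made a few days later, so some information arrives slightly later than an early call would have given it. No visit, procedure, treatment or sample-size change is needed.
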